#### 13.1.1 Blinded Interim Analysis

The original study SAP describes a blinded interim analysis and sample size re-assessment to occur when blinded MMN data from all 3 periods are available for 12 subjects, or when 20 subjects have been dosed and are expected to complete the study, whichever is sooner. An analysis structured identically to the Primary Analysis but blinded to treatment, will be performed. For this interim analysis, the MMN negative values closest to zero (i.e., most impaired) and the negative values farthest from zero (i.e., least impaired) for each subject will be selected and compared. This analysis will utilize the O'Brien-Fleming group-sequential stopping boundary to control alpha. SAS Proc SEQTEST will be employed to perform the conditional power analysis for one interim analysis. Study stoppage for futility may occur if conditional power is very low.

Additionally, prior to study stoppage, an assessment will be performed to calculate the conditional power values associated with protocol-permissible increases in the sample size (i.e., up to N=40), based on the observed blinded data at the time of the interim analysis

#### 13.1.2 Unblinded Interim Analysis

During the study, upon review of the outputs from the blinded interim analysis (which included data only from the first 12 subjects, who had already completed the study), the Sponsor determined that an unblinded analysis of those interim data is necessary to properly inform decisions about study continuation and dose selection. Unblinding of the interim analysis data is thus introduced in Protocol Amendment 4, and the SAP will be modified accordingly and finalized prior to the unblinded interim analysis.

An analysis unblinded to treatment and structured identically to the Primary Analysis will be performed using data only from the first 12 subjects, who have already completed the study. The analysis will consist of a comparison of the post dose PD parameter Mean Amplitude of Duration MMN versus the same parameter at time-matched placebo period timepoints. This analysis will utilize the O'Brien-Fleming group-sequential stopping boundary to control alpha.

SAS Proc SEQTEST will be employed to perform the conditional power analysis. Study stoppage for futility may occur if conditional power is very low.

Additionally, prior to study stoppage, the unblinded interim data will be used to calculate the conditional power values associated with protocol-permissible increases in the sample size (i.e., up to N=40), based on the observed unblinded data at the time of the interim analysis.

CONFIDENTIAL

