### **6.2.1 Dose Modification**

The dosages chosen at study outset, 15 mg and 150 mg, span a 10-fold range, with a large gap in between. If unblinded interim data suggest that either dosage is ineffective or poorly tolerated, the Sponsor may elect to discontinue use of that dosage and to replace it with another. The new dosage will not exceed 150 mg.

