## **8.5 Unblinding Procedure**

The investigational drug blind shall not be broken by the investigator unless information concerning the investigational drug is necessary for the medical treatment of the subject. All study assessments and assignment of causality for AEs should be performed, if possible, prior to unblinding. In the event of a medical emergency, if possible, the medical monitor should be contacted before the investigational drug blind is broken to discuss the need for unblinding.

For unblinding a subject, the investigational drug blind can be obtained by contacting the dispensing pharmacist.

The sponsor must be notified as soon as possible if the investigational drug blind is broken. The date, time, and reason the blind is broken must be recorded in the source documents and the same information (except the time) must be recorded on the eCRF.

If any site personnel are unblinded, investigational drug must be stopped immediately and the subject must be withdrawn from the study.

Having completed a blinded interim analysis of data for the first 12 completed subjects, the Sponsor has determined that those data will be unblinded per a change to the study plan introduced in Protocol Amendment 4. All data from subsequently enrolled subjects will remain blinded until the study is concluded.

No change should be made to any prior assessments or data of any subject after unblinding of his/her treatment assignment.

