### 13.1.3 Analysis Sets

#### *Safety Set*

The Safety Set will consist of all subjects who are randomized and receive study drug. Subjects in this analysis set will be used for demographic, baseline characteristics and safety summaries.

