#### *Pharmacodynamic Set*

The PD Set will consist of all subjects who receive study drug and have at least 1 post-dose PD measurement.

If any subjects are found to be noncompliant in dosing schedule or with incomplete data, a decision will be made on a case-by-case basis as to their inclusion in the PK and PD endpoint analyses, but data for all subjects will be presented in the subject listings.

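### Dose tolerability at the unblinded interim is judged on 12 completers only, so anyone who stopped because of a regimen is missing from that judgement

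*Protocol*

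**What the plan says.** Three sections of the current protocol text, which introduces the unblinded look through Amendment 4, fix the matter together.

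- **Section 13.1.2 (Unblinded Interim Analysis)** states that an unblinded analysis "structured identically to the Primary Analysis will be performed using data only from the first 12 subjects, who have already completed the study". It describes the comparison as duration MMN against placebo, and gives study continuation and dose selection as the purposes.
- **Section 8.5 (Unblinding Procedure)** defines what is unblinded: "Having completed a blinded interim analysis of data for the first 12 completed subjects, the Sponsor has determined that those data will be unblinded". It adds: "All data from subsequently enrolled subjects will remain blinded until the study is concluded".
- **Section 6.2.1 (Dose Modification)** states how the result is used: "If unblinded interim data suggest that either dosage is ineffective or poorly tolerated, the Sponsor may elect to discontinue use of that dosage", with substitution of a different one.

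The trigger in Section 13.1.1, "blinded MMN data from all 3 periods are available for 12 subjects, or when 20 subjects have been dosed and are expected to complete", points the same way.

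The analysis sets in Section 13.1.3 do not require completion. For safety: "The Safety Set will consist of all subjects who are randomized and receive study drug". For pharmacodynamics: "The PD Set will consist of all subjects who receive study drug and have at least 1 post-dose PD measurement". A further paragraph there leaves the inclusion of subjects with incomplete data in the PK and PD analyses to individual decision.

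Section 7.5 lists an adverse event, including unwillingness to continue because of one, as a reason for discontinuation. Sections 7.6 and 13.2 provide for replacing subjects who stop. Section 11.0 states that there is no data safety monitoring committee.

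**The concern.** Section 6.2.1 asks a tolerability question and answers it with data selected on having tolerated all three periods well enough to finish. The subjects most informative about poor tolerability, those who took a dosage and left because of it, are removed by the selection rule. Both their withdrawal and the adverse events that preceded it drop out of the comparison between regimens.

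If such subjects exist, the omission has a known direction: the dosage that drove them out looks better than it is. The decision is the sponsor's, no independent committee is planned, and no other section supplies by-regimen data on non-completers. At stake is whether a dosage is kept for later subjects on an incomplete tolerability record.

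**Working it through.** **1. Is there a stated figure to reproduce?** Not on this point: the protocol gives no expected discontinuation rate. Its power statement (20 subjects, d = 0.5, alpha 0.10, about 80%) is not an input here.

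**2. Who is in the unblinded data?** Set side by side:

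- Section 8.5 selects on completion.
- Section 13.1.2 confines the analysis to the same 12.
- Section 8.5 keeps subsequently enrolled subjects blinded.
- A subject enrolled among the first 12 completers who stopped early is neither one of the 12 nor subsequently enrolled. The text is silent on that subject, and no section brings their treatment assignment into the look.

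**3. What does this do to the tolerability data?** Among completers, the number who withdrew because of a regimen is zero at every dosage by definition, whatever the true rate. This follows from the selection rule and is not an observed result. Adverse events in subjects who stopped are absent for the same reason.

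**4. How many dosed subjects could be left out?** Assume each dosed subject stops early, for any reason, with probability p, independently of the others, and that the set closes at the 12th completer in enrolment order. The number of stoppers enrolled before that point is negative binomial:

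- expected number left out = 12p/(1 − p)
- chance of at least one = 1 − (1 − p)^12

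| Assumed p | Expected left out | Chance of at least one |
|---|---|---|
| 5% | 12 × 0.05/0.95 = 0.63 | 1 − 0.95^12 = 1 − 0.540 = 46% |
| 10% | 12 × 0.10/0.90 = 1.33 | 1 − 0.90^12 = 1 − 0.282 = 72% |
| 20% | 12 × 0.20/0.80 = 3.00 | 1 − 0.80^12 = 1 − 0.069 = 93% |

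These are all-cause figures. The number who stopped because of a regimen is some unknown part of them.

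**5. What would a fuller set show?** As an illustration, suppose all stopping were intolerability at one dosage, with true probability 10%, 20% or 30%. In a simulation over the six sequences, recruiting until 12 subjects completed, all dosed subjects together showed average withdrawal of about 9%, 19% or 28%. The completers show 0% in each case.

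**The case against.** There is a serious case on the other side, and much of it stands.

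**Tolerability is not only withdrawal.** Section 6.2.1 does not define poor tolerability by discontinuation. The safety endpoints in Section 5.2.2 are treatment-emergent events and clinically significant laboratory results. Both remain visible in 12 people who each received placebo and both dosages. So the judgement is incomplete rather than empty, and a zero withdrawal rate among completers is a tautology, not a measured understatement.

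**Other safety routes exist.** Adverse events in non-completers are collected and reported (Section 10.2), serious unexpected reactions are expedited (Section 10.3.1), and Section 6.3.1 allows stopping on new safety information. None of these is described as giving events and discontinuations by regimen for the Section 6.2.1 decision.

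**The range may be too high for intolerability.** Section 4.3 reports no discontinuation due to a treatment-emergent event in either earlier study. Section 6.2 describes the earlier phase 1 subjects as healthy, so this does not settle the rate in schizophrenia, but it is the only such evidence in the document.

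**Perhaps nobody is missing.** Section 13.1.2 could mean the first 12 enrolled, all of whom finished. The wording of Section 8.5 and the three-period trigger favour the completer reading. If the other reading is true, no harm arises.

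**The details could sit in the SAP.** Section 13.1.2 says that the SAP will be modified before the look. But the protocol itself fixes which data are unblinded, so a SAP that added discontinued subjects would go beyond it.

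**A stronger reading the documents do not support.** A reader might infer that futility and sample-size decisions are also distorted, because the interim excludes subjects whom the final analysis will include. Section 13.1.3 leaves inclusion of incomplete data to individual decision, and Sections 6.1 and 13.2 aim for completers with MMN in all three periods. The description of the interim as structured like the primary analysis reads naturally as the same model and contrast. With subject as a factor (Section 13.1.6), a one-period subject adds nothing to the treatment contrast and a subject with placebo and one active period adds one comparison. No change in conditional power, standard deviation or sample size has been shown.

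**Conclusion.** The point holds for the dose decision. Sections 8.5 and 13.1.2 confine the unblinded data to 12 completers, Section 6.2.1 judges tolerability on those data, and anyone who stopped because of a regimen is excluded by rule. The resulting bias favours the dosage concerned, if any such subject exists.

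The documents do not establish that one does. Under an assumed all-cause stopping rate of 5% to 20%, the chance that at least one dosed subject is left out is 46% to 93%, with 0.6 to 3.0 expected. The chance for intolerability alone is lower by an unknown amount. With no early stoppers the effect is nil.

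The point does not extend to futility or sample size, where a population mismatch is possible but is neither stated nor shown to matter.

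**What to change.** Reconcile Sections 6.2.1, 8.5 and 13.1.2, with matching SAP text, as follows.

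- **Tolerability input to the dose decision:** all Safety Set subjects enrolled no later than the last of the 12 completers who have either completed or permanently discontinued. Show treatment-emergent events and discontinuations by regimen.
- **Blinding:** subjects enrolled later, and those still in treatment, stay blinded. The enrolment limit is needed because a cut-off by date alone could unblind people who enrolled after the 12 and have already left, contrary to Section 8.5.
- **MMN and conditional power:** these may stay on the 12 completers. A PD Set version within the same cut-off is an optional sensitivity analysis.

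The cost is a few sentences and one by-regimen table, with no added subjects or procedures. The downside is unblinding the few subjects who have already discontinued. Because stoppers reach a final status sooner than completers, leaving out those still in treatment can slightly raise the apparent stopping share, so their number should be shown beside the table. No dosage or tolerability threshold is proposed.

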**Statistical Considerations:**

Observed values for the PD parameters (MMN and exploratory PD parameters) in each period will be summarized by treatment and compared to time matched assessments during placebo dosing using summary statistics. Comparison of post dose PD parameters to time matched placebo period timepoints will be analyzed using analysis of covariance (ANCOVA) with baseline value as a covariate and factors for sequence, subject nested within sequence, period, and treatment. Two-sided 95% confidence intervals will be constructed for the least squares mean differences between CVN058 and placebo in changes of PD parameters, comparing CVN058 and placebo at a time-matched post-dose time point.

Effect size will be calculated for comparisons of CVN058 to placebo using Cohen's  $d$  which expresses the difference between the means of 2 groups as a function of their pooled standard deviation.

Plasma PK concentrations and parameters of CVN058, and its metabolite if appropriate, will be listed and summarized by treatment using descriptive statistics. Exposure-response relationships for CVN058 will be explored graphically.

Adverse events (AEs) will be presented in listings, and treatment-emergent AEs (TEAEs) will be summarized by treatment. Individual results of vital signs will be listed and observed values and changes from Baseline in vital signs will be summarized by treatment.

Sample size re-estimation will occur after twelve (12) subjects have completed all study visits, or when 20 subjects have been dosed and are expected to complete the study, whichever is sooner. The sample size re-estimation will be performed using SAS® PROC POWER for Paired-Sample Means and specifications of power = 80%, alpha=0.10 and the unblinded group standard deviation values attained from the twelve study subjects.

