### 13.1.6 Pharmacodynamic Analysis

Observed values for the PD parameters (MMN and exploratory PD parameters) will be summarized by treatment and compared to placebo using summary statistics. Comparison of post-dose PD parameters from a time-matched placebo period timepoint will be analyzed using analysis of covariance (ANCOVA) with factors for sequence, subject nested within sequence, period, and treatment. Two-sided 95% confidence intervals will be constructed for the LS mean of observed differences in PD parameters, comparing CVN058 and placebo at a time-matched post-dose time point.

Effect size will be calculated for comparisons of CVN058 to placebo using Cohen's *d* which expresses the difference between the means of 2 groups as a function of their pooled standard deviation.

Exposure-response relationships for CVN058 will be explored graphically.

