## 13.2 Determination of Sample Size

Enrollment of 20 subjects with schizophrenia is estimated to provide approximately 80% power to detect a mean effect size of Cohen's *d*=0.5 with an error rate of alpha=0.10. Discontinued or withdrawn subjects and subjects for whom MMN is not available for all three study periods may be replaced. The sample size chosen of 20 completed subjects is considered to be sufficient to explore the changes in MMN between CVN058 and placebo as well as safety and tolerability of CVN058 in this population.

Sample size re-estimation may occur when MMN data from all 3 periods are available for 12 subjects, or when 20 subjects have been dosed and are expected to complete the study, whichever is sooner. To ensure adequate study power, sample size may be increased based on this re-estimation procedure. Further details will be included in the SAP.

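### The O'Brien-Fleming boundary named to control alpha at the unblinded look does not by itself guarantee the 10% rate when that look may also inform a larger N and a dose change, with two doses compared against placebo

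*Protocol*

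**What the plan says.** Section 13.1.2 introduces an unblinded analysis of the first 12 subjects, structured like the primary analysis, and relies on the O'Brien-Fleming "group-sequential stopping boundary to control alpha". The same section allows a futility stop, optional and with no threshold, and states that "the unblinded interim data will be used to calculate the conditional power values associated with protocol-permissible increases in the sample size". The maximum of 40 subjects is in that section and in the synopsis.

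Section 6.2.1 adds that if the unblinded data suggest a dose is ineffective or poorly tolerated, "the Sponsor may elect to discontinue use of that dosage and to replace it with another". In Table 8.b, regimens B and C keep their labels if the dosage is revised.

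The error rate comes from section 13.2: "Enrollment of 20 subjects with schizophrenia is estimated to provide approximately 80% power to detect a mean effect size", specified as a "mean effect size of Cohen's *d*=0.5", "with an error rate of alpha=0.10". It is not said whether 0.10 is one- or two-sided, or per comparison or familywise. Section 13.1.6 describes a single ANCOVA with sequence, subject, period and treatment, with no separation by stage, and adds: "Two-sided 95% confidence intervals will be constructed for the LS mean of observed differences in PD parameters".

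The synopsis, under Statistical Considerations, gives a different re-estimation method: "PROC POWER for Paired-Sample Means and specifications of power = 80%, alpha=0.10", using the unblinded group standard deviations.

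**The concern.** A group-sequential boundary keeps its error rate for one hypothesis and for information levels that do not respond to the observed effect. Three features of the plan fall outside that:

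- The final N may be informed by the unblinded effect, through conditional power.
- A dose may be replaced because its unblinded result looks poor.
- Each of two doses is compared with placebo.

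Nothing in the protocol's description of the analysis (stage weights, a conditional-error method, a test order or a primary dose) brings these back under the boundary. The section nevertheless names the boundary as the means of control. A positive MMN result could therefore be reported against a 10% rate that the described procedure does not deliver. The protocol also describes two routes to a new N, one from standard deviations and one from the observed effect, and does not say which governs.

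**Working it through.** **Inputs from the protocol.** N=20, d=0.5, alpha=0.10, about 80% power (13.2); interim after 12 subjects (13.1.2), so the information fraction is 12/20=0.6; maximum N 40; two doses sharing one placebo period per subject.

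**Assumptions.** Normal statistics; d taken as the standardised paired difference; correlation 0.5 between the two dose-minus-placebo contrasts; ordinary pooled final statistic. The rules for choosing N, swapping a dose and stopping for futility are assumed, because the protocol gives none.

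**1. Reproduce the stated power.** Paired t-test, 19 df, noncentrality 0.5×√20=2.236.
- One-sided 0.10: 81.7%, matching the stated figure.
- Two-sided 0.10: 69.5%; 80% would then need N=27.

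On this reading of d the stated power is one-sided, so one-sided 0.10 is the main case.

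**2. Boundary.** With two looks at fraction 0.6, one-sided 0.10, the critical values are c2=1.360 (final) and c1=1.360/√0.6=1.755 (interim).

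**3. Why choosing N from the effect matters.** Given interim z1, the null probability of crossing c2 at the end is 1−Φ[(c2√N − z1√12)/√(N−12)].
- z1=0: N=20 gives 1−Φ(2.150)=1.6%; N=40 gives 1−Φ(1.625)=5.2%.
- z1=0.5: N=20 gives 1−Φ(1.537)=6.2%; N=40 gives 1−Φ(1.298)=9.7%.
- z1=1.3: N=20 gives 1−Φ(0.558)=28.9%; N=40 gives 1−Φ(0.774)=21.9%.

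Extending after a weak interim result raises the chance of a false positive; extending after a strong one lowers it. A rule that extends mainly after weak results inflates the error.

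**4. Simulated error under the null (2,000,000 runs).** The N rules were: the smallest N from 20 to 40 giving 80% conditional power under the current trend, else 40; N=40 whenever conditional power at 20 is below 80%; and the N that maximises the conditional error. Swap rule: the worse dose is replaced if its interim z is below 0, and the new dose is tested on post-interim subjects only. Futility column: binding stop if conditional power at N=40 is below 10%.

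| Design | No futility stop | With futility stop |
|---|---|---|
| One dose, N=20 | 10.0% | – |
| One dose, N increase | 11.5-11.9% | 10.0-10.5% |
| Two doses, N=20 | 16.8% | 15.9% (conditional power taken at N=20) |
| Two doses, N increase | 19.2-19.6% | 17.5-17.9% |
| Two doses, N increase and swap | 22.8-23.3% | 18.5-19.0% |

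If futility is instead judged on conditional power at N=20, the one-dose error under the 80% rule is 9.9% (stop below 5%) or 9.4% (stop below 10%).

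**5. If 0.10 is two-sided.** With the boundary set at one-sided 5%, the one-direction error is 5.0% for one dose at N=20, 8.8% for two doses, 10.2-10.6% with the N increase and 12.4-12.8% with the swap. The pattern is the same.

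**6. Remedies for the N part, one dose.** The statistic √0.6·Z1 + √0.4·Z2, with Z1 from the first 12 subjects and Z2 from later ones, gives 10.0% whichever N is chosen. Allowing an increase only when conditional power at N=20 is at least 20% gives 9.8% under the 80% rule but just over 10% (10.1%) if N is chosen freely.

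**The case against.** Four points on the other side have weight.

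- **The SAP.** Section 13.1.2 says the SAP will be modified before the unblinded analysis, and 13.2 leaves re-estimation details to it. A combination test or test order may be there. A reader might infer that the trial has no error control; the protocol alone cannot show that. What stands is that the protocol names the boundary as the control, and for the design it describes that is not enough.
- **Familywise or per comparison.** A reader might infer that the true error is about double the stated 10%. That holds only if 0.10 is familywise, which the protocol never says, and the sentence on alpha concerns the interim look rather than multiplicity across doses. Read per comparison, the step from 10% to 17% is not inflation; only the N and dose-selection parts are.
- **Futility.** A stop at low conditional power removes most or all of the N effect. But it is optional and has no threshold, so it cannot be relied on.
- **How N is set.** Section 13.1.2 says conditional power will be calculated for larger N; it states no rule for choosing N. The only explicit formula is the SD-based one in the synopsis, which does not use the observed effect. This makes the size of the N effect uncertain, and it is why the two passages need reconciling.

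This is also a small phase 1 study with an exploratory aim. That supports a modest remedy, including the option of dropping the control claim.

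**Conclusion.** The point holds in a limited form: the boundary alone does not guarantee the 10% rate for the design described. On a one-sided test with assumed N rules, the unblinded increase adds about 1.5 to 2 percentage points for one dose, and little or nothing if a futility stop is applied. If 0.10 is familywise, the larger contribution comes from testing two doses, with the N increase and a swap adding to it; the total for all three, about 23%, depends on an invented swap trigger. All these figures are ranges under stated assumptions, not properties of a specified procedure. The conclusion concerns what the protocol claims, and it should be settled before the unblinded look.

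**What to change.** In section 13.1.2, with matching text in 13.2 and the synopsis:

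1. State whether 0.10 is per comparison or familywise, and whether it is one- or two-sided.
2. Test each retained dose with the fixed-weight combination of the first 12 and later subjects, weights √0.6 and √0.4, against the O'Brien-Fleming values. Do not substitute a minimum conditional power of 20% for an increase unless the rule for N is also fixed in advance.
3. If 0.10 is familywise, fix a testing order for the active regimens. Analyse any replacement regimen as its own treatment on post-interim subjects, not pooled under the old regimen label. Which dose is used is not a matter for this point.
4. Reconcile the SD-based re-estimation in the synopsis with the conditional-power assessment in 13.1.2, so that one governs N.

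Alternatively, delete the statement that the boundary controls alpha and label the final p-values nominal and exploratory.

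The cost is protocol and SAP wording, a small loss of efficiency if N is raised and, under a fixed order, a claim for the second dose only after the first succeeds.
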